9.1.2.1 Collection of Specimen(s)

These assessments will be made on circulating CLL and MCL, when possible, cells from the peripheral blood drawn from patients at baseline. These samples will be drawn either at screening or prior to study drug dosing on Cycle 1, Day 1, If we have bone marrow aspirates available, we will also perform BH3 profiling to see whether the level of priming in CLL cells from these tissues is a better predictor of response than peripheral blood CLL cells. Bone marrow aspirate sample is requested if bone marrow procedure is performed as standard of care or as part of protocol schedule. In addition, saliva as a source of germline DNA will be collected prior to study initiation and may be collected more than once if inadequate specimen is obtained. All samples will promptly be delivered to the laboratory of [name] (CLL patients) or [name] (MCL patients), where DNA will be extracted and then sent to the Broad Institute (Cambridge, MA) for whole exome sequencing.

After 1 week of treatment on Cycle 1, Day 8 (pre-dose), we will obtain another blood sample. We will compare the BH3 profile of this steady-state sample to a baseline sample, which will allow us to assess *in vivo* the short term change in apoptotic priming induced by these agents.

Version Date: 10.23.2019

Finally, a peripheral blood will be collected from subjects at the time of disease progression, and the BH3 profile of these samples will be compared to subjects' baseline samples to help identify whether a change in anti-apoptotic protein dependence is observed as a possible mechanism of resistance. A bone marrow sample at confirmation of complete response will be obtained and sent to Integrated Oncology for minimal residual disease assessment, while blood from the same time point is analyzed at the laboratory of [name] (CLL or SLL patients) or [name] (MCL patients). For the patients that have obtained a complete response, we request that peripheral blood samples be obtained every 6 cycles thereafter until disease progression, removal from study, or death.

9.1.2.2 Handling of Specimens(s)

All peripheral blood and bone marrow samples obtained at DFCI will promptly be refrigerated and delivered the same day as soon as possible to the laboratory of [name] or [name] at room temperature, where they will undergo Ficoll purification and then be viably frozen in FBS with 10% DMSO. The viably-frozen samples will be used for BH3 profiling assays (for detailed methods see (24).

Samples obtained from other institutions may either undergo Ficoll purification locally and then be viably frozen in FBS with 10% DMSO prior to shipment, or may be kept as whole blood and shipped on ice as soon as possible to [name] or [name] lab.

9.1.2.4 Site(s) Performing Correlative Study

All sites will be encouraged to provide the correlative samples for analysis, as feasible. While the goal of the biomarkers is to provide supportive data for the clinical study, there may be circumstances when a decision is made to stop a collection, not perform, or discontinue an analysis due to either practical or strategic reasons (e.g., inadequate sample number, issues related to the quality of the sample or issues related to the assay that preclude analysis, impossibility to perform correlative analyses, etc). Therefore, depending on the results obtained during the study, sample collection/analysis may be omitted at the discretion of the PI.

10. STUDY CALENDAR

Baseline evaluations / laboratory tests should be conducted within 21 days prior to C1D1. Scans used to identify measurable/evaluable disease are required to be done within 30 days prior to C1D1. In the event that the patient's condition is deteriorating, laboratory evaluations should be repeated within 48 hours prior to initiation of the next cycle of therapy. During cycles 12 and beyond, patients will be seen every 3 cycles (84 days +/- 7 days). After Cycle 36, participant have the option to return to the main research institution every 6 cycles (168 days +/-14 days) for full evaluation only if they are being followed every 3 cycles by a local oncologist. For full list of required assessments, please refer to section 5.4.10. After Cycle 15, scans will be performed approximately every 6 cycles (168 +/- 14 days) or more frequently, until C36 at which point they may be performed at the investigator's discretion until removal from treatment. Survival follow up should occur approximately every 3 cycles for up to 2 years, until death or next CLL/MCL-directed therapy, whichever occurs first.

Cycle = 28 days	Screeni ng	Cycle 1 (+-3 Days)		Cycle 1 (+-3 Days) Cycle 2 (Eve until ever u		Cycles 8+ (Every 2 cycles until C12, then every 3 cycles until C36 or beyond 11	Disease Progression/E nd of Treatment ^{9,10}	Follow Up (every 3 cycles for up to 2 years until new therapy, death, or withdrawal)			
Procedure \ Days	-21-0	Day 1	Day 8	Day 15	Day 22	Day 1	Day 15	Day 1	Day 1		
TGR-1202 Dose				I	Daily D	osing -	Days 1	-28			
Ibrutinib Dose				I	Daily D	osing -	Days 1	-28			
Survival Status ¹²											X ¹²
Informed consent	X										
Medical history	X	X	X	X	X	X	X	X	X	X	
Serum Pregnancy test	X*										
Physical examination	X	X	X	X	X	X	X	X	X	X	
Vital signs (pulse rate, BP, temperature)	X	X	X	X	X	X	X	X	X	X	
Urinalysis	X										
BM aspirate /biopsy ¹ , _{2,3}	X^3							$X^{2,3}$		$X^{2,3}$	$X^{2,3}$
SPEP + Immunoglobulins ⁴	X							X			
ECOG performance status	X	X	X	X	X	X	X	X	X	X	
EKG	X										
Serology: HIV, HCV, HBV	X										
CT scan (+/- 7 days)	X							X ⁵	X ^{5,6}	X	X ^{5,6}
Hematology	X	X	X	X	X	X	X	X	X	X	
Serum Chemistry	X	X	X	X	X	X	X	X	X	X	
PT/PTT/INR	X					X					
FISH Analysis /											
IGHV	X										
status/TP53/Zap70 7											
Correlative studies	X ^{8,3}	X	X							X^3	

Version Date: 10.23.2019

Cycle = 28 days	Screeni ng		Cycle 1 (+-3 Days)				Cycle 2 (+-3 Days)		Cycles 8+ (Every 2 cycles until C12, then every 3 cycles until C36 or beyond 11	Disease Progression/E nd of Treatment ^{9,10}	Follow Up (every 3 cycles for up to 2 years until new therapy, death, or withdrawal)
Procedure \ Days	-21-0	Day 1	Day 8	Day 15	Day 22	Day 1	Day 15	Day 1	Day 1		
Adverse Event Evaluation	X	X	X	X	X	X	X	X	X	X	
Concomitant Medication		X	X	X	X	X	X	X	X	X	

¹Unilateral bone marrow aspirate and/or biopsy required within 90 days prior to Day 1 of Cycle 1

M protein detected at baseline; If no M protein detected at baseline, IgG, IgA, IgM to be checked Cycle 3 and 6, 8, 10, 12, then every 3 cycles until Cycle 36, and every 6 cycles thereafter (B2M only at baseline)

² Only in patients who had a positive bone marrow prior to study initiation who achieve a radiographic CR, to confirm CR.

³ Marrow sample requested for correlative studies if bone marrow biopsy is done as standard of care, or as part of protocol schedule ⁴ SPEP required at baseline and then at Cycle 3 and 6, 8, 10, 12, then every 3 cycles until Cycle 36, and every 6 cycles thereafter only if

⁵ Just prior to cycle 3, then just prior to cycles 6, 10 and 15 (eg: C2D28, C5D28, C9D28, C14D28 +/- 7 days)

⁶ After C14D28 scans, CT scans should occur approximately every 6 cycles until C36 (+/- 14 days), then per investigator discretion thereafter

⁷ FISH for both CLL/SLL and MCL are to be done locally- IGHV, TP53 and Zap70 for CLL/SLL patients only (Integrated Onc.)

⁸ Baseline correlative studies may be obtained either at the screening visit or prior to study drug administration on C1D1.

⁹ End of treatment should be the next visit following a cycle after study drug was administered (within 3 days).

¹⁰ Patients are to be followed for survival and response every 3 months for up to two years or until death or other CLL/MCL directed therapy

^{*} Within 3 days of Day 1 / Cycle 1

[figure not shown]
 $^{^{11}}$ After cycle 36, participants may return to the main study site every 6 cycles (168 days+/-14 days) if they are being followed by a local hematologist/oncologist in the interim q3 cycles (84 +/-14 days). No study specific assessments need occur at the interim visits. Please see section 5.4.10 for additional information . Those who remain at the main research institution for all visits will continue to be seen every 3 cycles.

¹² Survival data may be collected by phone if necessary

^{*} Within 3 days of Day 1 / Cycle 1

11. MEASUREMENT OF EFFECT

Although response is not the primary endpoint of this trial, participants with measurable disease will be assessed by standard criteria. For the purposes of this study, the first efficacy assessment should be approximately 8 weeks after Cycle 1/Day 1 (+/- 7 days) and then just prior to cycles 6, 10 and 15. After cycle 15, efficacy assessments should occur at least every 6 cycles (168 +/- 14 days) until Cycle 36, where scans may be performed per investigator discretion.

11.1 Antitumor Effect

Assessment of lymphoma response (CR, PR or SD) and disease progression will be evaluated as outlined in the schedule of events, according to the Revised Response Criteria for Malignant Lymphoma for MCL and SLL patients (26) and for CLL patients, the IWCLL Response Criteria (27) as modified by (28).

11.1.1 Definitions

Evaluable for toxicity. All patients will be evaluable for toxicity from the time of their first treatment on Cycle 1/Day 1.

Evaluable for objective response. Only those patients who have had a pre-treatment baseline efficacy evaluation and at least one post-treatment efficacy evaluation will be considered evaluable for response. These patients will have their response classified according to the definitions stated below.

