	• If 1 DLT is reported in either Cohort 1, 2 or 3, an additional 3 patients will be enrolled. If no additional DLTs are reported ($\leq 1/6$ pts), then dose escalation will continue to the next cohort or Phase Ib (if in Cohort 3 already).
	• If at least two patients experience a DLT in either Cohort 1 (MCL or CLL/SLL), the combination dose will be considered above the maximum tolerated dose and the dose Cohort -1 will enroll 3-6 patients. The same DLT rules will apply for Cohort -1 except if 2/6 patients experience a DLT in Cohort -1 the study will end for that respective group. If at least two

patients experience a DLT in Cohort 2 or 3, the next highest dose level which has cleared DLT evaluation will be considered the dose for the Phase Ib part of the study.

Phase Ib:

Once the dose has been confirmed separately for MCL and CLL/SLL patients, the Phase Ib will open and enroll up to 12 additional patients. The efficacy evaluation will include the 6 patients from the Ph I cohort dose for up to approximately 18 total patients evaluable for efficacy in each patient group (MCL & CLL/SLL).

[figure not shown]
Each Cycle = 28 days Cycle 1:

- TGR-1202 (oral): Starting on Day 1 administered daily in the morning with food, preferably within 30 minutes of a meal
- Ibrutinib (oral): Starting on Day 1 administered daily in the evening

Cycles 2 and >:

Daily treatment with both TGR-1202 and ibrutinib should continue. First efficacy assessment should be approximately 8 weeks (just prior to cycle 3) after Cycle 1/Day 1 (+/- 7 days) and approximately every 12 weeks thereafter (+/- 7 days) through cycle 12 following initiation of therapy (schema below).

Treatment Study Visits

After cycle 12, regular visits should occur every 3 cycles. After the Cycle 15 restaging, disease assessments should occur at least every 6 cycles (+/- 14 days) through cycle 36, at which point assessments can be done per investigator's discretion. After removal from study, patients should be followed for survival approximately every 3 months for up to 2 years

Baseline Lab Evaluation (Local Lab)

- CBC with differential
- Serum chemistry
- Serology to rule out active Hep B, C or HIV infection
- Serum pregnancy test
- FISH cytogenetic analysis
- *IGHV* mutation status (CLL patients only- Test performed by Integrated Oncology- See correlatives section 9.1.2.3)

Instrumenta l Tests

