11.2 Response Criteria

See Appendix A for SLL and MCL. See Appendix B for CLL.

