13.2 Phase Ib

Once the MTD is established, an additional 12 eligible patients in each disease group will be treated at the MTD level to further evaluate the safety of TGR-1202 in combination of ibrutinib. The estimation of toxicity rate will be based on these 12 additional patients. With 12 patients, the 90% confidence interval of the toxicity rate will be within $\pm 25\%$.

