13.4 Analysis Plan for Secondary Objectives

Phase I/Ib Study of TGR-1202 plus Ibrutinib in Patients with Select B-Cell Malignancies Version Date: 10.23.2019

The secondary objectives include assessment of the overall response rate, nodal partial response rate, progression-free survival, and duration of response. Due to the exploratory nature, the analysis for secondary endpoints will largely be descriptive. Response rate and duration of response will be summarized descriptively and the Kaplan Meier method will be used to estimate the median progression-free survival time and progression-free survival. A similar descriptive analysis will be performed for laboratory correlative studies of BH3 profiling and pharmacodynamic markers such as phosphorylated levels of AKT, BTK, and ERK, as well as Ki-67 level. If feasible, association between clinical response and laboratory endpoints will be explored.

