APPENDIX B CHRONIC LYMPHOCYTIC LEUKEMIA RESPONSE DEFINITION (HALLEK ET AL. 2008)

Assessment of response should include a careful physical examination and evaluation of the blood and marrow.

CR requires all of the following criteria as assessed at least 2 months after completion of therapy:

- 1. Peripheral blood lymphocytes (evaluated by blood and differential count) below $4 \times 10^9 / L (4000 / \mu L)$.
- 2. Absence of significant lymphadenopathy (e.g., lymph nodes >1.5 cm in diameter) by physical examination.
- 3. No hepatomegaly or splenomegaly by physical examination and CT.
- 4. Absence of constitutional symptoms.
- 5. Blood counts above the following values:
 - Neutrophils >1.5 x $10^9/L$ ($1500/\mu L$) without need for exogenous growth factors.
 - Platelets >100 x 10^9 /L (100 000/ μ L) without need for exogenous growth factors.
 - Hemoglobin >110 g/L (11.0 g/dL) without red blood cell transfusion or need for exogenous erythropoietin.

For patients in clinical trials, a marrow aspirate and biopsy should be performed at least 2 months after the last treatment and if clinical and laboratory results listed above a-e demonstrate that a CR has been achieved. To define a CR, the marrow sample must be at least normocellular for age, with less than 30% of nucleated cells being lymphocytes. Lymphoid nodules should be absent. In some cases, lymphoid nodules can be found, which often reflect residual disease. These nodules should be recorded as "nodular PR." Moreover, immunohistochemistry should be performed to define whether these nodules are composed primarily of T cells or lymphocytes other than CLL cells or of CLL cells. If the marrow is hypocellular, a repeat determination should be performed after 4 weeks, or until peripheral blood counts have recovered. However, this time interval should not exceed 6 months after the last treatment. A marrow biopsy should be compared with that of pretreatment marrow. In general practice, the use of a marrow biopsy for evaluating a CR is at the discretion of the physician.

In clinical trials aiming at maximizing the CR rate, the quality of the CR should be assessed for MRD by flow cytometry or by immunohistochemistry.

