A controversial issue is how best to categorize the response of patients who fulfill all the criteria for a CR (including the marrow examinations described above) but who have a persistent anemia or thrombocytopenia or neutropenia apparently unrelated to CLL but related to drug toxicity. We recommend that these patients be considered as a different category of remission: CR with incomplete marrow recovery (CRi). For the definition of this category, CRi, the marrow evaluation (described above) should be performed with scrutiny and not show any clonal infiltrate. In clinical trials, CRi patients should be monitored prospectively to determine whether their outcome differs from that of patients with detectable residual or with noncytopenic CR.

Partial Response: (PR)

To define a PR (partial remission): at least two of the criteria of Group A plus one of the criteria of Group B have to be met. The parameters below should be documented for no less than 2 months. Constitutional symptoms persisting for >1 month should be recorded.

Group A

- a. Decrease in the number of blood lymphocytes by 50% or more from the value before therapy.
- b. Reduction in lymphadenopathy (by PE and CT scans) as defined by the following:
 - A decrease in lymph node size by 50% or more either in the sum products of up to 6 lymph nodes, or in the largest diameter of the enlarged lymph node(s) detected prior to therapy.
 - No increase in any lymph node, and no new enlarged lymph node. In small lymph nodes (<2 cm), an increase of less than 25% is not considered to be significant.
- c. Reduction in the noted pretreatment enlargement of the spleen or liver by 50% or more, as detected by CT scan.

Group B

- d. Blood count should show one of the following:
 - Neutrophils >1.5 x $10^9/L$ ($1500/\mu L$) without need for exogenous growth factors.
 - Platelet count >100 x 10⁹/L (100 000/μL) or 50% improvement over baseline without need for exogenous growth factors.
 - Hemoglobin >110 g/L (11.0 g/dL), or 50% improvement over baseline without requiring red blood cell transfusions or exogenous erythropoietin.

Chronic Lymphocytic Leukemia Response Definition (Hallek et al. 2008) (continued)

Progressive	Progressive disease during or after therapy is characterized by at least one of the	
Disease:	following:	

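### The plan implies an evaluable-only response rate with no all-treated rate beside it, which would overstate ORR if unassessed patients respond less often than assessed ones

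*Combined protocol and SAP*

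**What the plan says.** The combined protocol and SAP defines one population for response, in section 11.1.1: "Only those patients who have had a pre-treatment baseline efficacy evaluation and at least one post-treatment efficacy evaluation will be considered evaluable for response". The next sentence there gives a response classification to those patients only.

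The synopsis (Study Design, Phase Ib) adds the Phase I patients at the chosen dose to the Phase Ib patients and speaks of "up to approximately 18 total patients evaluable for efficacy in each patient group". Section 13.2, by contrast, is worded in treated patients: "an additional 12 eligible patients in each disease group will be treated at the MTD level".

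On analysis, section 13.4 says "Response rate and duration of response will be summarized descriptively". It gives no denominator, no all-treated rate and no rule for patients with no response assessment. The ORR definition in the synopsis and section 1.3, the best-overall-response rule in 11.2.3, and Appendices A and B do not supply one either.

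On timing, section 11 states that "the first efficacy assessment should be approximately 8 weeks after Cycle 1/Day 1", so two cycles of treatment come before the first scheduled assessment.

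**The concern.** Whether a patient is evaluable under 11.1.1 is settled by what happens after treatment starts (reading post-treatment there as after the first dose). A patient who dies, stops for toxicity or withdraws during the first two cycles may never be assessed, and would then be missing from both numerator and denominator. If such patients would have responded less often than the others, the reported rate is too high.

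The plan's other endpoints do not select in this way. Section 11.1.1 counts everyone from first treatment for toxicity. Section 11.2.5 runs PFS from registration and counts deaths. An early unassessed death is therefore a PFS event but absent from ORR. The replacement rule in 5.6.5 likewise does not return a replaced Phase I patient to any ORR denominator.

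What is at stake is how ORR is read. It is the first-named secondary efficacy measure, and a reader is likely to set it beside the single-agent ibrutinib rates in section 2.6 (71% in CLL/SLL, 68% in MCL).

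**Working it through.** **The plan's own figure.** 6 Phase I patients at the chosen dose + 12 Phase Ib patients = 18 per disease, which matches the synopsis. The plan sets no target, test or power for ORR, so there is no ORR sample size to reproduce.

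**Assumptions, not in the documents.** r = 12 responders among assessed patients; k = 1, 2 or 3 treated patients never assessed; p_u = the proportion of those k who would have responded. With k = 0 there is no bias.

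**Case A: 18 treated, of whom k are unassessed.** This fits the planned 6 + 12. All-treated ORR with p_u = 0 is 12/18 = 66.7%. Evaluable-only ORR is 12/(18 − k).

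**Case B: 18 evaluable plus k unassessed.** This follows the synopsis wording. Evaluable-only ORR is 12/18 = 66.7%. All-treated ORR with p_u = 0 is 12/(18 + k).

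| k | A: evaluable-only | A: excess over 66.7% | B: all-treated | B: shortfall from 66.7% |
|---|---|---|---|---|
| 1 | 12/17 = 70.6% | 3.9 points | 12/19 = 63.2% | 3.5 points |
| 2 | 12/16 = 75.0% | 8.3 points | 12/20 = 60.0% | 6.7 points |
| 3 | 12/15 = 80.0% | 13.3 points | 12/21 = 57.1% | 9.5 points |

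**Sensitivity to r.** With r from 9 to 14, one unassessed non-responder shifts ORR by 2.9 points (9/17 − 9/18) to 4.6 points (14/17 − 14/18) in case A. In case B the shift is 2.6 points (9/18 − 9/19) to 4.1 points (14/18 − 14/19).

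**Sensitivity to p_u, case B.** The bias of the evaluable-only rate is k/(18 + k) × (12/18 − p_u). For k = 1, 2, 3:
- p_u = 0: +3.5, +6.7, +9.5 points
- p_u = 1/3: +1.8, +3.3, +4.8 points
- p_u = 2/3: zero
- p_u = 1: −1.8, −3.3, −4.8 points

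**Bias of counting the unassessed as non-responders, case B.** This is −k × p_u/(18 + k). For k = 1, 2, 3:
- p_u = 1/3: −1.8, −3.3, −4.8 points
- p_u = 2/3: −3.5, −6.7, −9.5 points
- p_u = 1: −5.3, −10.0, −14.3 points

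Against the rate that would have been seen had everyone been assessed, the two rules err equally at p_u = 1/3. Below that, the non-responder rule is nearer.

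**Sampling error for scale.** The exact (Clopper-Pearson) 90% interval for 12/18 is 44.6% to 84.4%, 39.8 points wide.

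**The case against.** Most of the case on the other side bears on size and importance, and much of it stands.

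- **The denominator is inferred.** Section 13.4 does not prescribe an evaluable-only ORR. It names no denominator at all. That is correct. The reading rests on 11.1.1, the only response population defined, and on the synopsis wording.
- **Few patients may be affected.** The section 10 calendar marks a CT at progression or end of treatment, and its footnote 10 continues follow-up for response. In CLL, Appendix B says "Assessment of response should include a careful physical examination and evaluation of the blood and marrow", and examination and hematology are scheduled throughout the first two cycles (5.4.3 to 5.4.7). Many early leavers could therefore become evaluable. Patients who die or withdraw before any assessment, or who leave without a scan where one is needed, remain.
- **ORR is secondary and descriptive.** No threshold, test or decision depends on it, and the likely shift is small beside a 90% interval of about 40 points. This stands, although that interval does not allow for selective exclusion.
- **The comparison with 71% and 68% is loose.** Section 2.6 does not say which denominators those rates use. Phase I admits patients with prior BTK or PI3K inhibitors, and Phase Ib admits some MCL patients already on ibrutinib. This stands, so the comparison shows only how the figure may be read.

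Two stronger readings are tempting, and the documents do not support them.

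- A reader might infer that the non-responder rule is better founded in CLL, because Appendix B says of partial response "The parameters below should be documented for no less than 2 months". The criteria do differ by disease ("See Appendix A for SLL and MCL. See Appendix B for CLL"), but a patient with no post-treatment evaluation has no documented response under either appendix. The rule has the same standing in both diseases.
- A reader might take the gap between the two rates as the most by which the non-responder rule can understate response. It is not. At p_u = 1 the understatement in case B is 5.3, 10.0 and 14.3 points, against gaps of 3.5, 6.7 and 9.5. The gap is a ceiling only if the unassessed respond no more often than the assessed.

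**Conclusion.** The point holds, with a minor effect. Read naturally, the plan gives an evaluable-only ORR, and nothing in it supplies an all-treated rate. With one to three unassessed non-responders and 12 responders, the two rates differ by 3.9 to 13.3 points if 18 are treated, or by 3.5 to 9.5 points if 18 are evaluable. These sizes rest on assumed counts.

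The upward direction is conditional. It requires that unassessed patients would have responded less often than assessed ones; if they would have responded equally often, there is no bias. A reader might conclude that the trial's ORR is inflated, but the documents do not show that, because they say nothing about how many patients go unassessed or how those patients would have fared. No error rate, sample size or dose decision is touched.

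**What to change.** In sections 11.1.1 and 13.4:

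- Define the main ORR denominator as all patients with a baseline disease assessment who received at least one dose of the combination at the Phase Ib dose, including any replaced Phase I patients at that dose.
- Count patients with no post-baseline evaluation as not having a documented response, in both diseases.
- Report the evaluable-only ORR as supportive, with the numbers treated and evaluable and the reason for each exclusion.

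This costs a few sentences and needs no new data. The main ORR may be slightly lower, and it understates true response if some unassessed patients would have responded. The evaluable-only rate beside it bounds that understatement only if the unassessed respond no more often than the assessed.

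A separate matter: the section 10 calendar marks a CT at progression or end of treatment, while the list in 5.4.13 has none. The two entries should be reconciled.
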